5.4 Secondary outcomes measures

Secondary outcome measures include:

- Major adverse limb events (MALE) (defined as amputation or any major reintervention of the trial limb*)
- Major adverse cardiovascular events (MACE) (defined as recurrent CLTI, amputation affecting contralateral limb, acute coronary syndrome, ischaemic stroke)
- Bleeding Academic Research Consortium (BARC 2, 3 or 5) and Thrombolysis In Myocardial Infarction (TIMI) defined major bleeding
- Minor bleeding
- Primary and secondary patency of artery
- Reintervention
- Healing of tissue loss
- Health-related quality of life (VascuQoL-6 and EQ-5D-5L)
- Resource use, costs and cost-effectiveness
- Qualitative process evaluation, evaluating trial and intervention delivery through exploring trial conduct, trial acceptability (including barriers and facilitators to recruitment and retention), intervention adherence and contextual factors affecting trial delivery.
- * The term "trial limb" refers to the specific limb that will undergo the endovascular intervention for CLTI.

5.5 Separate exploratory/translational objectives and endpoints

Tertiary/exploratory outcomes include:

- MALE using other major definitions
- MACE using other major definitions
- Complications from trial medications
- Qualitative exploration of trial intervention implementation, feasibility and acceptability

6 Trial design and setting

6.1 Design

We will conduct a pragmatic, adaptive, multicentre, open-label, three-arm RCT, with internal pilot and adaptive interim analysis to examine the futility of the arm with the lowest predicted clinical effectiveness. The trial will evaluate the clinical and cost-effectiveness of three commonly used antithrombotic regimens following endovascular intervention for CLTI: once daily 75mg clopidogrel alone; once daily 75mg aspirin plus once daily 75mg clopidogrel; and once daily 75mg aspirin plus twice daily 2.5mg low-dose rivaroxaban. We plan to enrol 1,239 participants. This is a Type A Clinical Trial of Investigational Medicinal Product (CTIMP) as all 3 arms include only medicinal products within the licensed range of indications, dosage and form, and which are already given in routine clinical practice. We expect to reach the enrolment target within 36 months of starting recruitment. The study

will end 6 months after the date of the last data capture. Data collection will involve recording health outcomes, patient-reported outcome measures (PROMs) and serious adverse events in the electronic case report form (CRF) as well as questionnaires administered via telephone, videocall, email and post.

6.1.1 Setting

The trial will take place in inpatient settings in NHS hospitals at vascular units performing endovascular intervention for patients with CLTI in the United Kingdom (n=~20 sites). Eight lead centres (Bristol, Imperial, Guy's and St Thomas', St George's, Leeds, Newport/Cardiff and Vale, Hull, and Sheffield) will take part in the internal pilot. Further additional sites will be opened as required. If further sites are needed, those who are interested in participating in the trial will be required to complete a registration form to confirm that they have adequate resources and experience to conduct the trial.

6.2 Risk assessment

A Trial Risk Assessment has been completed to identify the potential hazards associated with the trial and to assess the likelihood of those hazards occurring and resulting in harm. This risk assessment has been completed in accordance with the Medical Research Council/Department of Health/Medicine and Healthcare products Regulatory Agency (MRC/DH/MHRA) Joint project guidance document 'Risk-adapted approaches to the management of Clinical Trials of Investigational Medicinal Products' and includes:

- The known and potential risks and benefits to human subjects
- How high the risk is compared to normal standard practice
- How the risk will be minimised/managed

This trial has been categorised as a Type A, where the level of risk is no higher than the risk of standard medical care. A copy of the trial risk assessment may be requested from the Trial Manager. The trial risk assessment is used to determine the intensity and focus of monitoring activity (see section 23.1).

This clinical trial is to be conducted in compliance with the protocol, the EU Clinical Trial Regulation 536/2014 and Good Clinical Practice (GCP).

7 Site and Investigator selection

This trial will be carried out at participating sites (n~20) within the UK. All sites who are interested in participating in the trial will be required to complete a registration form to confirm that they have adequate resources and experience to conduct the trial. Before any site can begin recruitment, a Principal Investigator (PI) at each site must be identified. Each site will have a co-investigator model consisting of a vascular surgeon and an interventional radiologist. Either of them may be the Principal Investigator. The following documents must be in place and copies sent to the CLARITY Trial email account (see contact details on page 3):

- Confirmation of Capacity and Capability (C&C) from the Research and Development (R&D) department following the sharing of local information pack
- Favourable opinion of host care organisation/PI from Main Ethics committee
- MHRA approval
- A signed Trial Agreement
- Current Curriculum Vitae and GCP training certificate of the PI
- Completed Site Delegation Log and Roles and Responsibilities document
- Full contact details for all host care organisation personnel involved, indicating preferred contact
- A copy of the most recent approved version of the Participant Information Sheet (PIS) and Consent Form(s) on host care organisation headed paper

- A copy of the most recent approved General Practitioner (GP) letter on host care organisation headed paper
- A copy of the most recent Pregnancy Information Sheet(s) and Consent Form(s) on host care organisation headed paper

Upon receipt of all the above documents, the Trial Manager will send written confirmation to the PI/lead Research Nurse detailing that the site is now ready to recruit participants for the trial. This letter/email must be filed in each site's Investigator Site File (ISF). Along with the written confirmation, the site should receive a trial pack holding all the documents required to recruit into the Trial.

Occasionally during the trial, amendments may be made to the trial documentation listed above. CTR will issue the site with the latest version of the documents as soon as they become available. It is the responsibility of the CTR to ensure that they obtain local R&D approval for the new documents.

The Trial Management Group (TMG) will apply for the trial to be registered with the Associate PI (API) scheme run by NIHR and will encourage the PI at each site to recruit a healthcare professional early in their research career to consider registering with the scheme.

Site initiation will be in person or by teleconference.

8 Participant selection

Patients undergoing percutaneous endovascular or hybrid intervention for CLTI of the lower limb may be assessed for eligibility.

Participants are eligible for the trial if they meet all of the following inclusion criteria and none of the exclusion criteria apply. All queries about participant eligibility should be directed to the Trial Manager before randomisation/registration using the CLARITY email address.

8.1 Inclusion criteria

- Adults (aged 18 years and over) undergoing percutaneous or hybrid endovascular intervention for CLTI of the lower limbs
- Atherosclerosis as the cause of CLTI
- Target arteries: infrainguinal (common femoral to pedal) if percutaneous, or iliac to pedal if performed as part of hybrid revascularisation with common femoral endarterectomy
- Clinicians would use trial antithrombotic combinations in normal clinical practice
- Able to provide informed consent
- First time in the CLARITY trial

8.2 Exclusion criteria

- Open lower-limb bypass as part of hybrid procedure
- Pre-existing clinical indication for dual antiplatelet therapy or anticoagulant e.g. atrial fibrillation
- Active malignancy or any other non-vascular condition associated with a life expectancy of less than 36 months
- Patients undergoing intervention to treat asymptomatic restenosis of a lower-limb bypass graft
- Embolic arterial disease
- Renal failure with creatinine clearance <15ml/minute

- Thrombophilia or any other inherited or acquired bleeding disorders
- Persons of childbearing potential* who have a positive pregnancy test, are breastfeeding or attempting pregnancy
- *A person is considered to be of childbearing potential i.e. fertile, following menarche and until becoming post-menopausal unless permanently sterile.
- Permanent sterilisation includes hysterectomy, bilateral salpingectomy and bilateral oophorectomy.
- A postmenopausal state is defined as no menses for 12 months without an alternative medical cause. A high follicle-stimulating hormone (FSH) level in the postmenopausal range may be used to confirm a post-menopausal state in women not using hormonal contraception or hormonal replacement therapy. However, in the absence of 12 months of amenorrhea, a single FSH measurement is insufficient.

In line with NICE guidelines on routine preoperative tests for elective surgery, including angioplasty, it is recommended to conduct pregnancy assessments for individuals of childbearing potential. Healthcare providers must sensitively enquire about the possibility of pregnancy on the day of surgery for all people of childbearing potential, ensuring they understand the risks to the foetus posed by anaesthesia and the procedure. In instances of uncertainty regarding pregnancy status, obtaining consent for a pregnancy test is advisable.

CLARITY has a pragmatic design which encourages all patient groups to be included. There is no inclusion or exclusion by protected group characteristics (other than pregnancy) and the design encourages inclusion of under-served patient groups who will benefit most from the treatment.

9 Recruitment, screening and registration

9.1 Internal pilot

An internal pilot is planned in the eight lead sites (including those where the CI/PI co-applicants are based). It will assess participant recruitment rates and the proportion of participants providing primary outcome data.

9.1.1 Recruitment rates

To confirm the recruitment rate, a retrospective audit of the Cl's unit (1.2 million population for CLTI; most UK vascular centres are now over 1 million) over 6 months in 2021 showed 103 patients treated endovascularly for CLTI in the trial arterial segments. A total of 41% would be excluded by our criteria (some in multiple categories: 20 (19%) for a pre-existing antithrombotic regimen, 15 (15%) for bleeding risk, 4 (4%) for renal failure, 5 (5%) for malignancy). This is higher than a published 30.7% exclusion estimate for the VOYAGER PAD trial from the Danish Vascular Registry (25). Assuming a pessimistic 30% enrolment rate, our centre would enrol 3 patients per month (26). Our sample size assumptions use a recruitment rate of 2 patients per site per month.

Pooled data from NIHR-funded studies show internal pilots typically recruit 15% of their participants within 33% of the total recruiting period (27). These figures have been used to calculate the number of participants expected to be recruited (n=186; 15% of 1239) by 9 months (24% of the total 36-month recruitment window).

A nine-month internal pilot (to take into account slower recruitment as sites first open) will start when the first centre is open to recruitment. The average recruitment rate would need to be 2.8 participants/site/month. The remaining recruitment time after the internal pilot is completed (27 months) would need to average 2.1 participants/site/month with 20 sites open. This takes into account smaller non-lead sites that will not see as many eligible patients and will recruit fewer

participants than the bigger lead sites. Also included in the progression criteria is the proportion of participants providing primary outcome data. The pilot has a challenging recruitment rate which is higher than the rest of the trial as we are opening a high number of sites early.

Table 1. Proposed internal pilot phase 9 months

Progression criteria	Red	Amber	Green
% Threshold for recruitment	<60%	60-99.9%	100%
Total number of participants recruited	<112	112-185	186
Recruitment rate/site/month	<1.59	1.59-2.64	>2.64
Number of sites open	<4	4-7	8
Participants providing primary composite and bleeding outcomes at 2 months	<70%	70-90%	>90%

If issues are identified regarding site opening or recruitment during the pilot phase, the trial qualitative researcher may attend a Vascular Surgery conference to discuss this with PIs. Additional data collection to explore reasons for low recruitment may also be conducted if necessary, which could include mapping the patient recruitment pathway, recording/observing recruitment discussions (with the permission of the patient and clinician), or analysis of documents such as trial meeting minutes.

There will be a planned review of the internal pilot at the 9-month time point. The results of this review will be discussed with the Trial Steering Committee (TSC) and fed back to the NIHR Health Technology Assessment (HTA) Programme.

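### The pilot and post-pilot recruitment rates in section 9.1.1 and Table 1 disagree with each other and with their stated inputs, and the rate's denominator is not defined

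*Protocol*

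**What the plan says.** The sample size is fixed in section 6.1: "We plan to enrol 1,239 participants". Section 9.1 names the pilot sites: "An internal pilot is planned in the eight lead sites". Section 9.1.1 gives the pilot target as "n=186; 15% of 1239) by 9 months (24% of the total 36-month recruitment window", and describes the pilot period so: "A nine-month internal pilot (to take into account slower recruitment as sites first open) will start when the first centre is open to recruitment". It then states two required rates. For the pilot: "The average recruitment rate would need to be 2.8 participants/site/month". For the remaining 27 months, recruitment "would need to average 2.1 participants/site/month with 20 sites open". A planning rate appears earlier in the same section: "Our sample size assumptions use a recruitment rate of 2 patients per site per month".

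Table 1 grades the pilot under column thresholds of 60% and 100%:

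- participants: red below 112, amber 112–185, green 186
- rate per site per month: red below 1.59, amber 1.59–2.64, green above 2.64
- sites open: green at 8

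The protocol does not say what the rate is divided by. It could be eight sites times nine months, or the months for which sites were actually open.

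**The concern.** The count row and the rate row of Table 1 sit under the same percentage thresholds, so they should be two expressions of one target. The text figure of 2.8 describes that target too. If the three do not share a denominator, one pilot result can receive two colours, or can be green in the table and still short of what the text calls necessary. A pilot averaging 2.7 is an example of the latter.

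The table is not decorative. The nine-month review goes to the Trial Steering Committee and the funder (end of section 9.1.1), and section 14.6 allows early termination if the funder judges the trial infeasible against these targets. The post-pilot rate is the benchmark that sites will be held to for three quarters of the recruitment window.

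**Working it through.** **Inputs.** Total 1239 (section 6.1). Pilot target 186, which is 0.15 × 1239 = 185.85 rounded up. Eight sites (section 9.1), nine months, then 27 months with 20 sites (section 9.1.1). Table 1 cut-offs 112 and 186 for count, 1.59 and 2.64 for rate. The lower count cut-off reproduces: 0.60 × 186 = 111.6, so 112.

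**Pilot rate on the nominal denominator.** 8 × 9 = 72 site-months.

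- 186/72 = 2.58, against 2.8 in the text and 2.64 in Table 1
- 112/72 = 1.556, against 1.59 in Table 1

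Converted back to participants:

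- 2.8 × 72 = 201.6, which is 8.4% above 186
- 2.64 × 72 = 190.1, which is 2.2% above 186
- 1.59 × 72 = 114.5, which is 2.2% above 112

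**Denominator implied by each stated rate.**

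| Stated rate | Participants | Implied site-months | Mean opening delay per site |
|---|---|---|---|
| 2.8 (text) | 186 | 186/2.8 = 66.4 | (72 − 66.4)/8 = 0.70 month |
| 2.64 (Table 1) | 186 | 186/2.64 = 70.45 | (72 − 70.45)/8 = 0.19 month |
| 1.59 (Table 1) | 112 | 112/1.59 = 70.44 | 0.19 month |

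The two Table 1 rates agree with each other. The text rate does not agree with them, and rounding does not close the gap. A value reported as 2.8 can lie between 2.75 and 2.85, which is 67.6 down to 65.3 site-months. A value reported as 2.64 lies between 2.635 and 2.645, which is 70.6 down to 70.3. Taking the pilot as 24% of 36 months gives 8 × 8.64 = 69.1 site-months and a rate of 2.69, which matches neither.

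**Colours on 72 site-months.**

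| Participants | Rate | Count row | Rate row |
|---|---|---|---|
| 111 | 1.542 | red | red |
| 112 | 1.556 | amber | red |
| 114 | 1.583 | amber | red |
| 186 | 2.583 | green | amber |
| 190 | 2.639 | green | amber |
| 191 | 2.653 | green | green |

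**Colours on open site-months.** 186 participants miss a rate above 2.64 only if site-months reach 70.45, that is, a mean delay of about 0.19 month (some 6 days) or less per site. As an illustration (this schedule is an assumption, not in the protocol), suppose the eight sites open a quarter of a month apart. Site-months are 72 − 0.25 × (0 + 1 + … + 7) = 72 − 7 = 65, and 186/65 = 2.86, which is green. The rows then part in the other direction: 172 participants give 172/65 = 2.65, green on rate and amber on count.

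**Post-pilot rate.** Remaining participants 1239 − 186 = 1053. Site-months 27 × 20 = 540.

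- 1053/540 = 1.95, against 2.1 stated
- 2.1 × 540 = 1134, which is 7.7% above 1053 and gives 1134 + 186 = 1320 in total
- 1053/2.1 = 501.4 site-months, or an average of 501.4/27 = 18.6 sites open

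Rounding does not explain this either: the lowest value that rounds to 2.1 is 2.05, and 2.05 × 540 = 1107.

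**The case against.** The strongest reply is that the protocol plainly expects sites to open over time. The pilot clock starts with the first centre, and the nine-month length is justified by slow early recruitment. On that view 72 site-months is the wrong denominator. The section also says many sites will open early, and the mean delays implied by the stated rates (0.2 and 0.7 month) are plausible for early opening. The 2.64 and 1.59 come from one denominator, which suggests an unstated opening schedule and not two slips. Likewise, 2.1 would follow if the 12 further sites opened on average (540 − 501.4)/12 = 3.2 months after the pilot. Finally, Table 1 guides a discussion; no single amber or red cell stops the trial.

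Much of this stands. A reader might infer that a pilot reaching exactly 186 participants fails its own green criterion. The document does not support that as a general statement: it holds on a fixed 8 × 9, or if all eight sites open almost at once. Nor can one say that staggered opening could never produce these figures, since each can be reached by some schedule. The Table 1 cut-offs should not be called arithmetic errors on a 2% difference from an assumed denominator.

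Two things do not yield. No single schedule gives both 2.8 and 2.64 for the same target. And the post-pilot sentence itself fixes 27 months and 20 open sites, which gives 1.95. The remark that smaller sites will recruit less explains variation between sites but cannot change the average that is required. The value 1.95 also sits close to the protocol's own planning rate of 2.

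**Conclusion.** The point holds as an internal inconsistency with an undefined denominator. The discrepancy between 2.8 and 2.64 needs no assumption beyond the shared target of 186. The discrepancy between 2.1 and 1.95 rests on taking the stated 27 months and 20 open sites literally. Measured against the nominal denominators, 2.8 and 2.1 are each about 8% too high; 2.64 and 1.59 are about 2% high and mutually consistent.

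The conflict in colours depends on the denominator chosen. On 72 site-months it is confined to 186–190 and 112–114 participants. On open site-months, 186 would normally be green on both rows, and disagreement appears below the target instead. The consequence is for the progression decision and the feasibility targets. The sample size of 1239 and the power calculation do not use these rates and are unaffected.

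**What to change.** Define the rate in Table 1 as participants divided by a stated number of site-months, and derive the text figure and both cut-offs from it so that 186 is green and 112 is amber on both rows.

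- If 72 site-months is intended: green at 186/72 or more (2.58); red below 112/72, written as a cut of 1.55; amber between; 2.6 in the text in place of 2.8. A red cut of 1.56 should be avoided, because 112/72 = 1.556 would still be red. With 1.55, 111 participants (1.542) are red and 112 are amber; with 2.58, 185 participants (2.569) are amber and 186 are green.
- If staggered opening is intended: state the schedule and its total site-months, and recompute the text figure and both cut-offs from that total.

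For the post-pilot period, change 2.1 to 1.95, or state the site-opening schedule that gives 2.1 and drop the statement that 20 sites are open throughout. In the same edit, 9 of 36 months should read 25%, not 24%.

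The cost is a handful of figures and one definition in section 9.1.1 and Table 1. No data collection, sample size or analysis changes. It should be done before the nine-month review, so that the thresholds are not settled with the pilot results in view.

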9.2 Participant identification

Patients listed for, or who are within 10 days of treatment of CLTI of the lower limb will be screened by members of the clinical care team against the above inclusion/exclusion criteria. Those who are considered potentially suitable for inclusion will be approached and provided with a PIS. The site PI, or suitably qualified medical practitioner who has been delegated the role, will confirm eligibility prior to consent.

For those who struggle to read, the PIS will be read to them. An opportunity will be given to them to ask questions. A trial infographic video/animation will also be developed.

Non-English language translation of participant-facing documentation (e.g., PIS and consent form(s), questionnaires), subtitles to the infographic videos/animations, and interpretation services such as 'Language Line' will be used where available, to ensure language is not a barrier to being considered for the trial.

Patients will ideally be approached before the endovascular procedure and then be randomised afterwards to start the trial medication as soon as clinically possible. It is acceptable to approach and randomise the patient following the procedure as long as the trial medication is started within 10 days of the procedure.

9.3 Screening logs

A screening log of all ineligible and eligible but not consented/not approached patients will be kept at each site so that any biases from differential recruitment will be detected. The screening log will be

integrated into the trial database for each site. When at the site, logs may contain identifiable information but this **must** be redacted before being sent to the CTR. The screening log should completed directly on the trial database or a copy of the paper version (if used) sent to [contact] every month (see section 23 for further details on data monitoring/quality assurance).

Once screened, participants not selected for recruitment due to polyvascular disease will be eligible to participate in the study within a trial (SWAT). A review of trial screening logs would identify patients with polyvascular disease and these will be approached by the research team for inclusion in the SWAT. Written informed consent will be received for the SWAT (consent for the SWAT will be distinct and separate from that of the main trial). The SWAT is detailed in section 17.

